5.2.7 Randomization revealed

After completion of standard of care, the study coordinator (or other authorized person) shall log-in to the EDC system to reveal whether the patient will receive Lumicell image-guided intervention. Randomization will be performed at a ratio of 10:1; for every 10 patients undergoing Lumicell imaging directed tissue resection after standard of care (“to proceed”), 1 patient shall complete surgery following standard of care alone (“not to proceed”). The randomization is intended to mitigate potential surgeon bias, and the 10:1 ratio was chosen based on prior clinical studies that supported imaging agent efficacy trials.

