- f. Mean and median incremental volume (in cubic centimeters) of tissue removed from therapeutic shaves: For each patient, absolute shave volume will be calculated as length (c) × width (c) × depth (c) for each therapeutic shave with the sum by patient of all therapeutic shaves. Subjects with no therapeutic shaves taken will have a therapeutic shave volume of 0cc.

- g. Mean and median contribution of therapeutic shave volume to total tissue removed.

LUMICELL CONFIDENTIAL

This document is confidential. Do not disclose or use except as authorized.

- h. Average number of SOC and therapeutic shaves taken per subject overall and by type of SOC lumpectomy procedure (i.e., lumpectomy with comprehensive shaves vs. lumpectomy with or without selective shaves).
- i. Number of second surgeries recommended as a result of final positive margins.
- j. Rate of second surgeries as a result of a positive margin status following SOC (control arm) and LUM Imaging procedures (device arm).
- k. Rate of cancer found in second surgeries
- l. Number of second surgeries for each patient
- m. Number of images per subject from the cavity after SOC and first round of therapeutic shaves
- n. Secondary analysis of sensitivity and specificity including imaging before removal of SOC shaves.
- o. Number of device issues and malfunctions and their impact to data capture.
- p. Patient-level sensitivity and specificity
- q. Collect exploratory data on tissue types found in therapeutic shaves.
- r. Collect exploratory data on patient reported outcomes.
- s. Analysis of tissue-level sensitivity and specificity for the SOC procedure based on the outermost SOC resected surface.
- t. Adverse events stratified by severity and relatedness to drug/device.
- u. Serious adverse events stratified by severity and relatedness to drug/device
- v. Adverse events by preferred term (sorted by descending occurrences for each preferred term).
- w. Summary of adverse events, overall and split by expectedness to drug/device.
- x. Comparison of adverse events in subjects that have at least one therapeutic shave versus subjects that have no therapeutic shaves.

4 Statistical methods

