4.7 Methods for additional analyses

Secondary outcomes involving proportions will be analyzed using methods for Binomial distributions akin to the ones described above. Continuous measurement will be summarized using means and standard deviation and 95% confidence intervals. The percent of people with a specific AE will be reported in prespecified groups. The percent of subjects with adverse events in subjects that have at least one therapeutic shave will be compared with the percent of subjects with adverse events that have no therapeutic shaves using Fisher's exact test or goodness of fit test.

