4.8 Safety analysis

Safety data will be reported as:

- Adverse events (AEs) stratified by severity and relatedness to drug/device.
- List of serious adverse events.
- Summary of AEs overall, by expectedness and by drug/device
- Adverse events coded per MedDRA guidelines
- Adverse events by preferred term per MedDRA (sorted by descending occurrences for each preferred term).
- Comparison of AEs in subjects that have at least one therapeutic shave versus subjects that have no therapeutic shaves
- Summary of AEs in system organ class and preferred terms (per MedDRA) and stratified by severity and relatedness to drug/device

All adverse events will be evaluated and assigned the "expectedness" by a Lumicell representative as described in the study plans or protocols and will be reported accordingly.

Two safety analyses sets will be completed: one for all the patients injected with LUM015 across all the clinical studies summarized in **Error! Reference source not found.**, and another one for just the breast cancer patients.

The safety variables of interest are listed below.

- AE and adverse device effects

LUMICELL CONFIDENTIAL

This document is confidential. Do not disclose or use except as authorized.

- Complete blood count
 - Platelet Count
 - Red blood cell Count
 - Hemoglobin
 - Hematocrit
 - Mean corpuscular volume
 - Mean corpuscular hemoglobin
 - Neutrophils
 - Lymphocytes
 - Monocytes
 - Eosinophils
 - Basophils
 - White blood cell count
- Serum chemistry
 - Albumin
 - Alkaline Phosphatase
 - Total Bilirubin
 - Blood urea nitrogen
 - Calcium
 - Chloride
 - Creatinine
 - Estimated glomerular filtration rate (eGFR)*
 - Glucose
 - Potassium
 - Total Protein
 - SGOT (AST)
 - SGPT (ALT)
 - Sodium

*Lumicell will calculate eGFR based on CKD-EPI Creatinine Equation per Levey et al [4]:

$$eGFR = 141 \times \min\left(\frac{S_{cr}}{K}, 1\right)^{\alpha} \times \max\left(\frac{S_{cr}}{K}, 1\right)^{-1.209} \times 0.993^{age} \times 1.018(\text{if female}) \\ \times 1.159(\text{if black})$$

Abbreviations / Units:

- eGFR = estimated glomerular filtration rate in mL/min/1.73 m²
- S_{cr} = serum creatinine in mg/dL per data entered in the CRF
- $K = 0.7$ (females) or 0.9 (males)
- $\alpha = -0.329$ (females) or -0.411 (males)

The resulting table with the calculated eGFR will be recorded as an external dataset.

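### The only adverse event comparison with a named test is by whether a therapeutic shave was taken; no summary by randomised arm is explicitly planned, and one should be added

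*SAP*

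**What the plan says.** SAP 4.7 sets the comparison: "The percent of subjects with adverse events in subjects that have at least one therapeutic shave will be compared". The other group is everyone without such a shave, and the choice of test is left open as Fisher's "exact test or goodness of fit test". SAP 3.3 lists it as secondary endpoint x, "Comparison of adverse events in subjects that have at least one therapeutic shave versus subjects that have no therapeutic shaves", and SAP 4.8 repeats it: "Comparison of AEs in subjects that have at least one therapeutic shave versus subjects that have no therapeutic shaves". Protocol 2.2 and 15.4.3 carry the same item as endpoint h. No significance level, sidedness, hypothesis or adjustment is given.

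The other safety outputs in SAP 4.8 are descriptive: severity, relatedness, expectedness, MedDRA terms, a list of serious events and laboratory variables. SAP 4.7 also says "The percent of people with a specific AE will be reported in prespecified groups", but does not say which groups. The general rule in SAP 4.11 is to summarise overall, by type of standard-of-care (SOC) surgery and by site. Arm is used elsewhere in the SAP: baseline data are shown by arm (4.1), and so are second surgeries (3.3, item j).

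Protocol 5.2.7 states "Randomization will be performed at a ratio of 10:1", device to control, with the arm revealed only once SOC surgery is complete. Under Protocol 5.2.8 and 5.3.1 and SAP 4.11.3, a therapeutic shave then requires assignment to the device arm, a positive LUM reading, enough tissue to remove, and a surgeon who follows the guidance.

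**The concern.** Shave status is not assigned by randomisation. It is an outcome of the imaging step, the anatomy of the cavity and a surgical decision. Any of these may also be related to the risk of an AE, in which case the two groups would differ in AE rate even if shaving caused no events at all.

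The comparison group is also a mixture. It contains every control patient and every device-arm patient without a shave, including those whose images were all negative. If the comparison is run in the safety population, it also contains dosed patients who could not be imaged.

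Showing safety is part of the stated objective, and Protocol 11.3 names infections and hematomas as events to watch for. Allocation is concealed until SOC surgery is finished, so the two randomised arms should be comparable up to that point. If AEs are never shown by arm, that information goes unused, and a reader is left with a contrast that could show a false excess or hide a real one.

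**Working it through.** The plan gives no AE rate, power or sample size for this comparison, so there is no figure to reproduce. I checked who falls in each group, what selection could do, and how precise a by-arm summary would be.

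**1. Arm sizes.** SAP 1.1 gives 406 enrolled; Protocol 5.2.7 gives 10:1. Controls: 406/11 = 36.9, about 37. Device arm: 406 − 37 = 369. The actual counts by arm are not in the documents.

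**2. Make-up of the no-shave group.** Let f be the share of the device arm with at least one shave. It is not given. SAP 4.3.2 reports a Phase C mean of 1.1 shaves; if counts were Poisson (an assumption), f = 1 − exp(−1.1) = 0.67. The shave group is 369f, the no-shave group is 406 − 369f, and the control share of the latter is 37/(406 − 369f).

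| f (assumed) | Shave | No shave | Controls among no-shave |
|---|---|---|---|
| 0.40 | 148 | 258 | 14% |
| 0.67 | 246 | 160 | 23% |
| 0.90 | 332 | 74 | 50% |

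Over most of this range the test is mainly a comparison within the device arm.

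**3. What selection could do (illustration; every rate is assumed).** Half of patients carry a risk factor. AE probability is 30% with it and 15% without, and shaving has no effect on AEs. In the device arm, shave probability is 80% with the factor and 40% without.

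- Shave group AE rate: (0.5×0.8×0.30 + 0.5×0.4×0.15)/0.6 = 0.15/0.6 = 25.0%.
- No-shave group: with the factor, 203 − 0.5×369×0.8 = 55.4; without it, 203 − 0.5×369×0.4 = 129.2. AE rate: (55.4×0.30 + 129.2×0.15)/184.6 = 36.0/184.6 = 19.5%.

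The spurious difference is 5.5 points, and Fisher's test at an assumed two-sided 0.05 rejects about 24% of the time. With shave probabilities of 70% and 50%, the rates are 23.75% and 21.0%, a difference of about 2.7 points, and it rejects 8.9% of the time. With equal shave probabilities it rejects 4.3%. A factor acting the other way would reverse the sign.

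**4. Precision by arm.** Half-width = 1.96 × √[p(1 − p)(1/369 + 1/37)], the same assumed rate p in both arms:

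- p = 0.10: 10.1 points
- p = 0.20: 13.5 points
- p = 0.30: 15.5 points

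Exact Fisher power (two-sided 0.05, control versus device, assumed rates) is 20% for 20% versus 30%, and 67% for 20% versus 40%. For a rare serious event, none among 37 controls leaves an exact two-sided 95% upper limit of 1 − 0.025^(1/37) = 9.5%. A by-arm table therefore serves estimation, not a powered test.

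**5. What the by-arm contrast measures.** All eligible subjects receive LUM015 (Protocol 5.1). Before the arm is revealed, the stepwise procedure has cavity initialization imaging (5.2.5) and an image at each site of a planned SOC shave (5.2.6). Only the post-SOC scan and therapeutic shaves are reserved for the device arm (5.2.8). A footnote to the Schedule of Events ties intraoperative imaging to the device arm, but the stepwise procedure does not.

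**The case against.** The best defence is that the shave contrast answers its own question: are there more AEs in patients who actually had extra tissue removed? The arm contrast dilutes that with device-arm patients who had no shave. Protocol 5.2.7 says that randomisation was meant to limit surgeon bias, not to supply a safety comparator. The test is one of 24 secondary items, has no success criterion, and sits beside descriptive tables and review by the Medical Monitor and the DSMB.

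The larger groups may also outweigh some bias. With 221 versus 185 patients and a 22.5% AE rate, the shave contrast has a standard error of √[0.225×0.775×(1/221 + 1/185)], or 4.2 points. Adding the assumed biases of 2.7 and 5.5 points gives root mean squared errors of about √(4.2² + 2.7²) = 5.0 and √(4.2² + 5.5²) = 6.9. The arm contrast has a standard error of 7.2 points. Stronger confounding would reverse that ranking.

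Nor do the documents link shave status to AE risk. Tumor burden looks a weak driver of shaving: Phase C averaged 1.1 shaves per patient, yet only 26 of 230 (11.3%) had cancer in any shave.

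These points stand as reasons to keep the shave table and to avoid claiming a known bias. They do not argue against adding a by-arm table, nor do they make shave status a randomised comparison.

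**Conclusion.** The point holds as a gap in the safety analysis. The one AE comparison with a named test uses a post-randomisation grouping, its reference group mixes arms, and no by-arm AE summary is explicitly listed. SAP 1 calls the study single-arm while the protocol describes two randomised arms; that may explain the omission but does not remove it.

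A reader might infer more than the documents support:

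- **That the shave contrast is known to be distorted.** It is open to selection bias, but neither size nor direction can be derived; the figures in step 3 rest on assumed rates.
- **That the arm contrast isolates all harm from the device.** Controls also receive LUM015 and pre-reveal imaging, so it reflects only the post-SOC scan and therapeutic shaves. Drug safety is uncontrolled under either grouping.
- **That a by-arm AE report is ruled out.** SAP 4.7 leaves its reporting groups undefined; the fault is that arm is not named.
- **That the choice of test is a substantive error.** The goodness of fit wording is probably a loose name for Pearson's chi-square, so naming one test is editorial.

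No primary endpoint or decision rule is affected. The by-arm estimate would be free of selection on shave status but imprecise: a half-width of about 13.5 to 15.5 points, assuming 369 versus 37 patients and AE rates of 20% to 30%.

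**What to change.** In SAP 4.7 and 4.8:

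1. Add AEs and SAEs by randomised arm in the safety population, with the risk difference and 95% confidence interval. Name an interval method suited to 37 controls and few events. Present this as estimation, not as a powered test.
2. State that this contrast reflects the post-SOC scan and therapeutic shaves only, because both arms receive LUM015 and the imaging done before the arm is revealed.
3. Define the groups for AE reporting in SAP 4.7 and name randomised arm as one of them.
4. Keep the shave versus no-shave table, labelled descriptive and non-randomised, and show it within the device arm. That removes the mixing with controls but not the selection, and the label should say so.
5. As an edit, replace the choice of two tests with one named test, or drop the test.

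The cost is one further set of tables from data already collected, and a wide interval that must be read as such. If AEs by arm have already been seen, label the tables as added afterwards.

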4.8 Safety analysis

Safety data will be reported as:

- Adverse events (AEs) stratified by severity and relatedness to drug/device.
- List of serious adverse events.
- Summary of AEs overall, by expectedness and by drug/device
- Adverse events coded per MedDRA guidelines
- Adverse events by preferred term per MedDRA (sorted by descending occurrences for each preferred term).
- Comparison of AEs in subjects that have at least one therapeutic shave versus subjects that have no therapeutic shaves
- Summary of AEs in system organ class and preferred terms (per MedDRA) and stratified by severity and relatedness to drug/device

All adverse events will be evaluated and assigned the "expectedness" by a Lumicell representative as described in the study plans or protocols and will be reported accordingly.

Two safety analyses sets will be completed: one for all the patients injected with LUM015 across all the clinical studies summarized in **Error! Reference source not found.**, and another one for just the breast cancer patients.

The safety variables of interest are listed below.

- AE and adverse device effects

LUMICELL CONFIDENTIAL

This document is confidential. Do not disclose or use except as authorized.

- Complete blood count
 - Platelet Count
 - Red blood cell Count
 - Hemoglobin
 - Hematocrit
 - Mean corpuscular volume
 - Mean corpuscular hemoglobin
 - Neutrophils
 - Lymphocytes
 - Monocytes
 - Eosinophils
 - Basophils
 - White blood cell count
- Serum chemistry
 - Albumin
 - Alkaline Phosphatase
 - Total Bilirubin
 - Blood urea nitrogen
 - Calcium
 - Chloride
 - Creatinine
 - Estimated glomerular filtration rate (eGFR)*
 - Glucose
 - Potassium
 - Total Protein
 - SGOT (AST)
 - SGPT (ALT)
 - Sodium

*Lumicell will calculate eGFR based on CKD-EPI Creatinine Equation per Levey et al [4]:

$$eGFR = 141 \times \min\left(\frac{S_{cr}}{K}, 1\right)^{\alpha} \times \max\left(\frac{S_{cr}}{K}, 1\right)^{-1.209} \times 0.993^{age} \times 1.018(\text{if female}) \\ \times 1.159(\text{if black})$$

Abbreviations / Units:

- eGFR = estimated glomerular filtration rate in mL/min/1.73 m²
- S_{cr} = serum creatinine in mg/dL per data entered in the CRF
- $K = 0.7$ (females) or 0.9 (males)
- $\alpha = -0.329$ (females) or -0.411 (males)

The resulting table with the calculated eGFR will be recorded as an external dataset.

4.9 Reported device issues

LUMICELL CONFIDENTIAL

This document is confidential. Do not disclose or use except as authorized.

Device issues as reported or interpreted by the clinical site are captured in the eCRF. An external dataset will be created to evaluate and adjudicate by Lumicell personnel for impact to subject safety, impact to data capture, and categorization. Issues that resulted in an impact to data capture may be removed from the efficacy analysis. The ‘Device Issues’ external dataset will be used for analysis and not generated by the device issues reported in the eCRF.

4.10 Protocol Deviations

Protocol Deviations are identified by either Lumicell personnel or clinical sites and reported in the eCRF. An external dataset will be created to evaluate and adjudicate these events by Lumicell personnel as described in the study plans and procedures. The adjudication will include whether there was impact to data capture and integrity, and may be indicate data to be removed from the efficacy analysis. The Protocol Deviations external dataset will be used for analysis and not generated by the protocol deviations reported in the eCRF.

4.11 General considerations

All analyses will be performed under Good Clinical Practice (GCP) standards using a prespecified statistical analysis plan (SAP). Analyses will be conducted and tables and listings generated using Statistical Analysis System (SAS®) Version 9.4 or higher. Graphics may be prepared with SAS Version 9.4 or higher; R version 3.6.1 or higher, SigmaPlot 12.3 or higher. Subject level data will be provided as a listing to support tables and figures. Summaries will be provided overall, by SOC surgery type (lumpectomy/selective vs comprehensive), and by site.

4.11.1 Numerical Precision

For reporting of descriptive statistics, the mean, SD, median, min, max and quantile will be presented to 1-digit precision. The minimum, median, and maximum will be presented to the same precision as the source data. The maximum number of decimals will be two, no matter how precise the source data is. The percentages will be reported to 1 decimal (format of xx.x%). Sensitivity and specificity will be reported as percentages with 1-digit precision (format of xx.x%). P-values will be reported to three (3) decimal places or as < 0.001.

4.11.2 Multiple images to cover entire shave or multiple shaves for one image

To accurately evaluate the study endpoints, it is critical that images are collected from the entire lumpectomy cavity surface. To achieve this, multiple images may be required to record the LUM assessment for an entire orientation (e.g. 2 images to cover the entire superior orientation) but a single shave may exist. When multiple images exist for a given orientation or shave, the combination of the images will be considered as one single output as described below:

- All images for a given orientation or shaved region are LUM negative, then the LUM result for the entire orientation or shaved region is considered as LUM negative.
- If one or more of the images for a given orientation or shaved region is LUM positive, then the LUM result for the entire orientation or shaved region is considered as LUM positive.

When there are more than one shave for a single image, the pathology finding for the combination of the shaves will be considered as one as follows:

LUMICELL CONFIDENTIAL

This document is confidential. Do not disclose or use except as authorized.

- If no tumor is found on the shaves, then the combination of the shaves is considered as truth standard negative.
- If any of the shaves has tumor, then the combination of the shaves is considered as truth standard positive.

4.11.3 Missing and spurious data

During LUM-guided imaging, when there is not enough tissue to be removed (e.g. too close to skin or too close to the chest wall) no LUM image shall be recorded because it does not generate an actionable result.

In the case where the LUM Imaging System indicates that a therapeutic shave needs to be removed but the surgeon decides not to follow this guidance, the reason for not doing so will be recorded in the patient's CRF or during imaging. These instances are considered as a protocol deviation. There are other cases when the LUM-guide shave reach the protocol limit of 2 guided shaves per orientation, so a third guided shave will not be performed. In these cases, the data will be included in the performance evaluation as is; that is, because these will not generate a LUM-guided shave they will not be evaluated as removing cancer or converting positive margins to negative margins. However, they will be evaluated for the per-tissue sensitivity and specificity calculation according the hierarchical approach described in section 3.2.2.

In occasions, a cavity image may be recorded from an unintended region or the image may be deemed as low quality (blurry, out of focus, etc.). For example, the surgeon realizes that he/she placed the device in the wrong location within the cavity after recording an image. Since the LUM software does not allow to overwrite saved images, the error images will be labeled as "image error delete", and the image will be excluded from the analysis.

Other specific cases will be handled as described below.

- a. When a patient was prescribed Letrozole adjuvant therapy prior to surgery, the patient will be removed from the device performance evaluation (major protocol deviation) in the per-protocol analysis but will be included in the mITT population for primary analysis.
- b. When the time from injection of LUM015 to initial imaging time is greater than 6 hours due to unplanned surgical delays, the patients will be removed from the device performance evaluation (major protocol deviation) in the per-protocol analysis but will be included in the mITT population for primary analysis.
- c. For the re-excision rate endpoints, all patients undergoing a re-excision will be included in the analysis.
- d. In the case of a therapeutic shave taken but no image saved before the shave was removed, the shave will be excluded from analysis but will be included in the estimation of final margin.
- e. In the case of a SOC shave taken but no image saved before the shave was removed, the shave will be excluded from analysis but will be included in the estimation of SOC margin.
- f. In the case of a protocol deviation where an SOC shave is taken after use of the LUM Imaging System, the analysis will be as follows:

LUMICELL CONFIDENTIAL

This document is confidential. Do not disclose or use except as authorized.

- i. For per tissue sensitivity and specificity: if there is a Lumicell image for this SOC shave, then the SOC shave will be used as truth standard for that orientation. If there is no Lumicell image, then the SOC shave will not be used for sensitivity and specificity evaluation.
- ii. For margin assessment analysis: for the calculation of the SOC margin status versus the margin status after Lumicell, the margin of that SOC shave will be excluded.
- g. In the case of a patient having bilateral lumpectomy, only the data collected from the side of the breast that was imaged will be included in the device performance evaluation.
- h. In the case of an unknown dimension of a shave, the volume of the shave will be assigned as the average volume of that of all the existing shaves of the corresponding type (SOC or therapeutic shaves).

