5.2.8 Lumicell procedure (only patients randomized to the intervention arm)

After the standard of care is completed for patients randomized “to proceed” with the Lumicell intervention, the surgeon will scan the tumor bed to collect images of the cavity walls and remove therapeutic shaves as indicated by the LUM decision software (refer to the Instructions For Use manual for details). The software will automatically turn on the tumor detection algorithm to allow visualization and navigation of the lumpectomy cavity with highlighting of suspected tumor by the tumor detection algorithm.

5.2.8.1 When there is no tissue available to be removed from a given orientation (e.g., too close to skin or too close to the chest wall), no LUM image shall be collected from that orientation. This information must be documented.

5.2.8.2 The surgeon shall scan the cavity and generate images from each orientation. Images should be generated and saved for both LUM positive and negative results.

5.2.8.3 The surgeon shall take a Lumicell shave from each imaged location indicated as “positive” by the LUM decision software.

5.2.8.4 A maximum of two (2) Lumicell shaves may be taken from any one orientation. Additional Lumicell shaves beyond 2 per orientation will constitute a protocol violation.

5.2.8.5 The resected tissue(s) shall be handled and named according to the Appendix B.

If a shave is not taken when indicated by the LUM Imaging System or a Lumicell image is not recorded as described above, a protocol deviation will be recorded with exception as described in section 5.3.1. If images are not saved in all orientations, a protocol deviation will be recorded unless there is no enough tissue left to take a shave (see 5.2.8.1). The reason for not taking a shave when indicated by the Lumicell system shall be recorded.

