3.2 Three co-primary endpoints

3.2.1 Removal of residual cancer

Ratio of patients who have **residual cancer** found in at least one LUM-guided shave (also known as therapeutic shave or “T-shaves”) among all patients randomized to the device arm. **Residual cancer** is defined as tumor found by pathology in a therapeutic shave after the SOC surgical procedure is completed; that is, tumor that current SOC surgery failed to remove (Figure 1). Mathematically, it is defined as:

$$\frac{\# \text{ patients with residual cancer found in at least one therapeutic shave}}{\text{Total number of patients}}$$

[figure not shown]

Figure 1: Depiction of primary endpoint

[figure not shown]
This proposed primary endpoint for determination of whether tumor is found in at least one therapeutic shave, the **ground truth** of histopathology assessment of the therapeutic shave is used.

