3.2.2 Sensitivity and specificity

The instrument diagnostic accuracy is measured by sensitivity and specificity on a per-tissue basis. Because a LUM-guided shave does not exist when a negative LUM image is indicated we propose a hierarchical approach to determine the truth standard as depicted in Figure 2. The highest truth standard is whether pathology finds cancer in a tissue shave removed from the area that was imaged in the cavity. When a shave does not exist, then whether tumor is found in a re-excision surgery is considered as the truth standard. When neither a shave nor a second surgery exists for a given orientation that was imaged, the margin assessment of that orientation is used as truth standard. We believe that the hierarchical approach outlined to determine the truth standard is the most meaningful and practical assessment of device accuracy to predict the presence of cancer in the cavity.

LUMICELL CONFIDENTIAL

This document is confidential. Do not disclose or use except as authorized.

True positive = truth standard positive & Lum cavity image positive
 False negative = truth standard positive & Lum cavity image negative
 True negative = truth standard negative & Lum cavity image negative
 False positive = truth standard negative & Lum cavity image positive

Figure 2: Definition of truth standard to evaluate the LUM Imaging System diagnostic performance.

When a therapeutic shave and re-excision are not available for a given orientation, the margin from the prior resected tissue of the corresponding orientation will be used as ground inferred truth for evaluation (Figure 3). The number of prior positive margins contributing to the ground inferred truth for a patient will not exceed the number of orientations with positive margins.

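### SAP 4.11.3 d excludes a therapeutic shave with no saved image from all analysis except the final margin, which conflicts with the residual-cancer co-primary and other endpoints that need no image

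*SAP*

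**What the plan says.** SAP 4.11.3 lists special cases. Rule d reads: "In the case of a therapeutic shave taken but no image saved before the shave was removed, the shave will be excluded from analysis". It continues with a single exception: the shave is dropped "but will be included in the estimation of final margin". Neither part says which analyses are meant. Neighbouring rules do state a scope. Rules a, b and g refer to the device performance evaluation, rule c to re-excision rates, and rule f separates per-tissue accuracy from margin assessment.

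The endpoints themselves do not depend on a saved image:

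- Residual cancer (SAP 3.2.1) is "tumor found by pathology in a therapeutic shave after the SOC surgical procedure is completed".
- Shave volume (SAP 3.3 f) is computed "for each therapeutic shave with the sum by patient of all therapeutic shaves", and "Subjects with no therapeutic shaves taken will have a therapeutic shave volume of 0cc".
- The count in SAP 3.3 h is "Average number of SOC and therapeutic shaves taken per subject overall".

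On the image itself, Protocol 5.2.8 says that if a shave is not taken when indicated, "or a Lumicell image is not recorded as described above, a protocol deviation will be recorded". Protocol 15.4.6, which covers missing data, has no counterpart to rule d.

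**The concern.** A programmer who follows rule d literally will drop the shave from every endpoint except margin status. Cancer found in it would leave the residual-cancer numerator while the patient stays in the denominator, so a co-primary would depart from its own definition. The same holds for secondary endpoints d and e.

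For tissue removal the result is inconsistent. The shave can still be credited with converting a positive margin (b, c), but its volume, its share of total tissue and its count disappear (f, g, h). Its histology drops out of q. A patient whose only guided shave lacks an image has no remaining shave to sum, and she may be placed with the patients without therapeutic shaves in the adverse-event comparison (x). The benefit of the shave is then kept while the tissue taken to obtain it is not reported.

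**Working it through.** **1. Which endpoints need an image?**

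| Endpoint | Unit of evidence | Image needed? | Under rule d as written |
|---|---|---|---|
| Residual cancer (co-primary), d, e | pathology of a therapeutic shave | no | dropped |
| b, c | margin status after the LUM procedure | no | kept by the exception |
| f, g, h | dimensions and number of shaves | no | dropped |
| q, x | histology; whether a shave was taken | no | dropped |
| Per-tissue sensitivity, specificity | LUM image against truth standard (SAP 3.2.2) | yes | dropped |

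Only the last row gives a reason for exclusion. Rule h of the same section imputes the volume of a shave with unknown dimensions, whereas rule d drops one whose dimensions are known.

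**2. Inputs.** The assumed residual-cancer rate is 9% against a goal of 3%, with 220 patients and one-sided 2.5% (SAP 4.2). Phase C had 1.1 guided shaves per patient, about 10% of resected tissue (SAP 4.3.2), and 26 of 230 patients with residual cancer (SAP 4.2). There are 1021/152 = 6.717 truth-standard negatives per patient (SAP 4.5). The share f of therapeutic shaves without a saved image is not given; I assume 3%, 5% and 10%.

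**3. The plan's own figure.** With n = 220, the exact binomial test of 3% rejects at 13 or more patients (one-sided level 0.0163). Power at 9% is 96.4%. This reproduces the 96% in SAP 4.5. SAP 4.2 states 90% for the same 220 patients; that difference does not bear on this point.

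**4. Effect of rule d on endpoints that need no image.**

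- Shaves per patient: 1.1 × (1 − f).
- Volume falls by the fraction f if the affected shaves are of average size.
- Share of total tissue: with a true share of 10 parts in 100, it becomes 10(1 − f) / (100 − 10f) if the shave is dropped from both parts.
- Residual cancer, worst case of one tumor-bearing shave per affected patient: 9% × (1 − f).

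| f | Shaves per patient | Fall in volume | Share of tissue | Residual-cancer rate | Power, n = 220 |
|---|---|---|---|---|---|
| 0 | 1.10 | none | 10.0% | 9.0% | 96.4% |
| 3% | 1.07 | 3% | 9.7% | 8.7% | 95.2% |
| 5% | 1.05 | 5% | 9.5% | 8.6% | 94.2% |
| 10% | 0.99 | 10% | 9.1% | 8.1% | 91.1% |

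**5. Accuracy: is the direction known?** SAP 3.2.2 says "Because a LUM-guided shave does not exist when a negative LUM image is indicated", so every unit that rule d removes is LUM-positive. Phase C suggests that about 10% of guided shaves contain tumor: 26/(1.1 × 230) = 10.3%, assuming one such shave per cancer patient. About 1.1 × 0.9 = 0.99 per patient are therefore benign. If only these were lost, a true specificity of 65% (4.366 true negatives out of 6.717) would become 4.366/(6.717 − 0.99f), which is 65.3%, 65.5% and 66.0% at the three values of f.

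LUM-negative orientations with no saved image also fail to enter the 2×2 table, and those with negative truth are lost true negatives. Specificity stays at 65% when true negatives and false positives are lost in the ratio 65:35. The balancing loss is 0.99f × 0.65/0.35 = 0.055, 0.092 and 0.184 true negatives per patient, or 1.3%, 2.1% and 4.2% of the 4.366. Above those rates specificity falls, and below them it rises. The documents give neither rate.

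**The case against.** The strongest reply is that rule d was meant only for image-based accuracy. It stands among rules on image handling. Rule e uses the same words for SOC shaves, and it is implausible that the SAP meant to delete SOC tissue from total tissue removed. Rule f.i limits its own no-image exclusion to sensitivity and specificity, and rule h shows a wish to count all removed tissue. This may well be the intent, but rule d does not say so, and naming one exception implies that there are no others. If this is the intent, the fix only records it.

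A second reply has real force. A therapeutic shave is one taken under LUM guidance, and without a saved image nothing stored shows that the display was positive there. Counting cancer in such a shave credits the device on a co-primary without that record. This is why the residual-cancer result should be shown both ways.

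A reader might make three stronger inferences that the documents do not support:

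- *The rule inflates specificity.* A unit without an image cannot enter the 2×2 table under SAP 3.2.2 whatever rule d says, and unsaved LUM-negative orientations are lost as well. The net direction is unknown.
- *The rule favours the device throughout.* Its effect on residual cancer works against the device, and losing true positives would lower sensitivity.
- *The SAP assigns 0 cc to an affected patient.* The 0 cc rule covers patients in whom no therapeutic shave was taken, and she had one. Rule d and endpoint f conflict, and the SAP does not say which prevails.

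**Conclusion.** The point holds as a conflict between an unscoped rule and the endpoint definitions. Followed literally, rule d gives wrong values for the residual-cancer co-primary and for endpoints d to h, q and x, while b and c are protected by the final-margin exception. Tissue removal and the residual-cancer rate are both understated.

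The size rests on an unsaved-image rate that the documents do not give. At an assumed 3% to 10%, shave number and volume fall by about 3% to 10%, provided affected shaves are of average size. A 9% residual-cancer rate falls by at most 0.3 to 0.9 points, with power still above 90% at 220 patients. The true rate may be low, because an unrecorded image is a protocol deviation. No claim is made about the net bias in specificity. The correction is worth making because it is cheap and affects how a co-primary is computed.

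**What to change.** Amend SAP 4.11.3 d as follows:

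- Limit the exclusion to per-tissue sensitivity and specificity.
- State that the shave still counts in the residual-cancer co-primary and in endpoints d to h, q and x. Endpoints b and c need no change.
- Report the number of therapeutic shaves with no saved image and how many contain tumor. SAP 1.1 already refers to 406 enrolled patients, so these should be countable.
- Show the residual-cancer result with and without these shaves, because no stored image documents the guidance.
- Add one sensitivity analysis of per-tissue accuracy that counts each such shave as LUM-positive with its own pathology as truth.

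The cost is a short SAP edit, a count and one extra run, with no change to trial conduct. Tissue-removal figures may become slightly less favourable, and the residual-cancer rate can only stay the same or rise.
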